## Analysis Plan

For Aim 1 and Aim 2 will calculate frequencies and proportions and means and standard deviations (or medians and interquartile ranges if variables are non-normal) to assess feasibility and acceptability outcomes. T-tests or chi-square will be used to compare eligible patients who did and did not enroll, and those who enrolled and dropped out, on demographic and clinical variables. Exit interviews will be audio recorded, transcribed, and iteratively analyzed using

thematic content analysis in NVivo 11. Transcripts will be reviewed by two members of the study team to identify themes and develop a coding framework. Discrepancies in coding will then be resolved through discussion.

For Aim 3, we will examine frequency distributions for each exploratory outcome at each timepoint and use non-parametric tests if needed. We plan to use linear mixed effects models with repeated measures and an unstructured covariance matrix to assess changes over time for each psychological and behavioral variable (separate dependent variables). The predictor variables will be time (fixed effect: up to 16 levels across pre-post intervention surveys and daily diaries or actigraphy) and covariates relevant for each dependent variable (random effects). If there are any time effects, we will conduct follow up analyses to determine if those effects show a change over the course of the intervention period in the expected direction. We will create change scores (post-intervention survey minus pre-intervention survey) and explore correlations of changes in psychological variables with changes in behavioral variables. Missing data will be imputed using maximum likelihood estimation and, as a sensitivity analysis, the last observation carried forward. Given the exploratory nature of the proposed pilot study, we will focus the interpretation of Aim 3 analyses on effect sizes (Cohen's d) rather than statistical significance to assess potential signals for intervention effects.

For studies involving treatment or diagnosis, provide information about standard of care at Mass General Brigham (e.g., BWH, MGH) and indicate how the study procedures differ from standard care. Provide information on available alternative treatments, procedures, or methods of diagnosis.

All study participants will continue to receive standard care. The study procedures differ from standard care in that patients will be approached about the study and invited to participate. Those who are eligible and interested in participating will receive training in an evidence-based skills building program with their peers and a trained instructor. All patients who choose to participate in the study will continue to receive standard care with no other differences in their treatment beyond additional training in psychosocial skills. The alternative is to continue standard care without also participating in the study intervention.

Describe how risks to subjects are minimized, for example, by using procedures which are consistent with sound research design and which do not unnecessarily expose subjects to risk or by using procedures already being performed on the subject for diagnostic or treatment purposes.

To minimize risks, all procedures will be performed in clinically stable participants who meet eligibility criteria. Participant risks are mitigated by excluding participants who are particularly vulnerable including those with severe mental illness, or those who are cognitively impaired, have short life expectancy. Participants will also be told that all participation is voluntary, and they can withdraw from the study at any time. Also, they will be told that the care they receive from their treating providers will in no way be affected by their participation or decision not to participate in this study.

Any serious adverse events (SAEs) will be reported to the IRB. SAEs will be collected and reported from screening to 30 days after the end of the study follow-up period for an individual participant. SAEs will be followed until resolution, stabilization, or until it is determined that study participation is not the cause.

Describe explicitly the methods for ensuring the safety of subjects. Provide objective criteria for removing a subject from the study, for example, objective criteria for worsening disease/lack of improvement and/or unacceptable adverse events. The inclusion of objective drop criteria is especially important in studies designed with placebo control groups.

As the intervention is psycho-educational in nature, and participants do not need to physically come to the hospital to participate in any study procedures, there is no risk of physical injury to participants. Participation is voluntary for all subjects. As explicitly stated in the informed consent documents, participants may withdraw from participation at any time by notifying study staff. Participants will not be required to provide a reason for withdrawal. Participants will be reminded that they can withdraw from the study at any point during their participation.

The main safety concern related to patients in this study is worsening psychological symptoms. Subject safety regarding psychological symptoms will be ensured per the protocol below.

The study therapist conducting the intervention session will be a trained clinician with a PhD in clinical psychology and expertise in the MBCT protocol. Thus, the study therapist will have expertise in assessment and treatment of mental health disorders and will be trained to identify if participants are experiencing severe psychological distress and can intervene if needed. The interventionists will observationally monitor participant's symptoms during each weekly intervention session. If the interventionists become concerned based on a participant's presentation during a session (e.g., per their clinical observation or expressed SI by a participant), they will call the participant by phone individually immediately after the session to check in about the participant's symptoms and conduct a safety assessment if needed. The interventionists will instruct patients at the start of the first session that if they experience worsening mood symptoms or concerns for their safety (e.g., suicidal thoughts) at any point during the study, they should let the interventionist, study staff, and/or their doctors know. At the start of the first session, we will (a) instruct participants that the group will be discussing emotional resiliency after SCAD and not medical details of SCAD, (b) instruct participants not to share personal details of their SCAD or relive their SCAD experience within the group, and (c) ask participants to share 1 positive coping skill they are using for their emotional well-being. The interventionist will interrupt any participants who overshare details of their SCAD and re-direct the discussion to positive coping. Participants will be instructed to call or email the research assistant (a) if they experience significant distress after the first session, or (b) if they experience any difficulties with the intervention throughout the study and would like an individual check in with the interventionist. In both cases the interventionist will call the patients for assessment and intervention if needed. Should a participant express suicidal ideation at any time during the study, the study clinician will immediately assess the subject and determine the appropriate course of action. Options for addressing suicidal ideation will include contacting the individual's treatment provider, referring for urgent (same day) evaluation and treatment in an outpatient clinic, or emergency room evaluation and hospitalization. Similar practices will be used for other emergencies, including but not limited to psychosis, homicidal or violent thoughts, or an acute change in a subject's physical status. The study PI ([name]) and two of the study Co-Is (Drs. [name] and [name]) are both licensed psychologists; Co-I [name] is a board-certified cardiologist. All of these members of the study team will be available to discuss and respond to concerns of participant safety over the course of the study.

The objective criteria for removal from the study is worsening psychiatric symptoms that become psychiatrically unstable that precludes their participation (e.g., constitute danger to self or others). The PI will let the participants know that if it seems unsafe for them to remain in the study, the PI will contact them. In cases where psychological symptoms are worsening but do not constitute necessary removal from the study, the PI will discuss the concerns with the participant, give them the option to exit the study if they would like, and assist them in connecting to a higher level of care if needed (e.g., by providing mental health referrals).

To ensure the physical safety of participants, we will inform treating cardiologists that physical activity will be tracked as part of the study and obtain approval that it is safe for the participant to

be applying intervention skills to increased physical activity. Following guidelines from a 2018 AHA scientific statement on SCAD, we will advise SCAD patients in the trial to avoid prolonged high-intensity activities, highly competitive or contact sports, activities performed to exhaustion, abrupt increases in physical activity without warm-up, and exercising in extreme temperature.

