## **RESEARCH DESIGN AND METHODS**

Briefly describe study design and anticipated enrollment, i.e., number of subjects to be enrolled by researchers study-wide and by Mass General Brigham researchers. Provide a brief summary of the eligibility criteria (for example, age range, gender, medical condition). Include any local site restrictions, for example, "Enrollment at Mass General Brigham will be limited to adults although the sponsor's protocol is open to both children and adults."

The current study will employ an open pilot trial to determine the initial feasibility and

acceptability of a targeted, virtual UpBeat-MBCT intervention for SCAD survivors. We plan to enroll approximately N=20 participants (approx. n=8 survivors/group, accounting for 20% anticipated lost to follow-up). The UpBeat-MBCT intervention will involve 8 MBCT sessions (approximately 1.5 hours each) delivered via synchronous group videoconference, which combines cognitive-behavioral therapy, mindfulness meditation, and cardiac health behavior promotion. During each session, participants will be taught how to use evidence-based mindfulness skills to reduce fear of recurrence and promote positive health behaviors (and physical activity). We will hold two intervention cohort groups that will be run sequentially. Participants in the intervention will be asked to complete a full survey battery of the measures before and after the intervention, and wear an actigraphy device (e.g., to measure physical activity and sleep patterns) for 7 consecutive days within the 1-2 weeks before and after the intervention. In addition, participants will be asked to complete a daily diary of abbreviated measures for 1-2 weeks before and after the intervention. Upon completion of the intervention, participants will complete an audio- or video-recorded exit interview (approx. 45-60 minutes).

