**Measured Outcomes:**

The primary outcomes are feasibility and acceptability of the intervention and research procedures. The exploratory outcomes are changes in psychological and behavioral variables, measured via pre-post intervention surveys, and daily diaries and actigraphy each day for 1-2

weeks before and after the intervention. Daily diaries will include psychological variables and self-reported physical activity (collected at night) and sleep outcomes (collected at morning). Covariates will be extracted from the medical record, including date of SCAD event, pregnancy-associated SCAD, medical and psychiatric comorbidities, cardiac rehab attendance, and hospital readmissions. Please refer to tables 1 and 2 below for details of feasibility and acceptability outcomes (Table 1) and exploratory outcomes (Table 2).

Table 1. PRIMARY OUTCOMES (Aims 1 and 2)	
Feasibility	
Enrollment	≥70% of eligible enroll; <20% ineligible due to each criterion; reasons for ineligibility; reasons for refusal; characteristics of refusers
Retention	≤20% participant attrition
Intervention components	≥70% session attendance; fidelity score ≥70%; ≤20% of sessions missed due to videoconference problems; ≤20% connections dropped during session; number (M≤2.0) and types of videoconference problems
Surveys	≥70% pre-intervention and post-intervention surveys completed; ≥70% daily diaries completed for 7 consecutive days; ≤20% missing data on daily diaries
Actigraphy	≥70% completed 7 consecutive days
Acceptability	
Intervention components	Program satisfaction (M≥7.0), ≥70% plan to use the skills, ≥70% would recommend the program to others ( post-survey ); likes, dislikes, suggestions for program improvement ( exit interview )
Surveys	Ease of survey completion (1=not at all, 10=extremely M≥7.0); level of interference (1=not at all, 10=extremely M≤2.0; post-survey ); experiences, challenges, suggestions for improvement ( exit interview )
Actigraphy	Ease of actigraphy completion (1=not at all, 10=extremely M≥7.0; post-survey ); experiences, challenges, suggestions ( exit interview )

Table 2. EXPLORATORY OUTCOMES (Aim 3)		
Psychological Variables	Measurement	Model Component
Non-judgmental body awareness	Multidimensional Assessment of Interoceptive Awareness	Intervention mechanism
Attention regulation	Cognitive Affective Mindfulness Scale-Revised	Intervention mechanism

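### Chi-square is planned for a dropout comparison of about 4 versus 16 participants, where expected counts are too small for it; an exact test should be named instead

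*Combined protocol and SAP*

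**What the plan says.** For Aims 1 and 2 the Analysis Plan describes the feasibility and acceptability outcomes with proportions, means or medians. It then adds one inferential step: "T-tests or chi-square will be used to compare eligible patients who did and did not enroll, and those who enrolled and dropped out". The traits compared are clinical and demographic. The plan does not name the group with which dropouts are compared; completers is the natural reading. It does not say whether chi-square means the uncorrected Pearson test or the continuity-corrected one. It states no significance level.

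Research Design and Methods fixes the scale: "We plan to enroll approximately N=20 participants (approx. n=8 survivors/group, accounting for 20% anticipated lost to follow-up". It also says "We will hold two intervention cohort groups that will be run sequentially". Table 1 sets the retention benchmark at "≤20% participant attrition".

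On the traits that might be compared, Measured Outcomes says: "Covariates will be extracted from the medical record, including date of SCAD event, pregnancy-associated SCAD, medical and psychiatric comorbidities". No frequencies are given.

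Two statements in the Analysis Plan could look like safeguards: "we will examine frequency distributions for each exploratory outcome at each timepoint and use non-parametric tests if needed" and "we will focus the interpretation of Aim 3 analyses on effect sizes (Cohen's d) rather than statistical significance". Both are written for Aim 3 and do not reach the dropout comparison.

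**The concern.** The chi-square p-value is a large-sample approximation that becomes unreliable when expected cell counts are small. Here they are small by design, because a study that meets its own retention benchmark with 20 enrolled has at most 4 dropouts. For an uncommon trait, a single participant can decide the result.

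What is at stake is modest but real. This is the only statistical test the plan names for describing who leaves the study. Several traits may be compared, and no multiplicity rule is given. A pilot report could therefore name a predictor of dropout that rests on one person.

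**Working it through.** **Inputs.** Two groups of about 8, 20% loss and about 20 enrolled (Research Design and Methods). Chi-square with no version stated (Analysis Plan). Assumed, because the documents are silent: a 5% significance level, completers as the comparator, and a range of trait prevalences.

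**1. The plan's own figure.** 2 × 8 = 16 retained, and 16 / (1 − 0.20) = 20, which matches the stated enrollment. The comparison is therefore 4 dropouts versus 16 completers.

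**2. Expected counts.** With K carriers among 20, the dropout row has expected counts 4K/20 and 4(20 − K)/20. They sum to 4, so both are below 5 whatever K is. The carrier cell is below 1 when 4K/20 < 1, that is K < 5, or prevalence under 25%.

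**3. One carrier, who is a dropout (1/4 versus 0/16).**
- Pearson: χ² = 20 × (1×16 − 3×0)² / (4 × 16 × 1 × 19) = 5120/1216 = 4.211, p = 0.040.
- Fisher: the chance that the sole carrier falls among the 4 dropouts is 4/20, so p = 0.20.
- Yates correction: χ² = 20 × (16 − 10)² / 1216 = 0.592, p = 0.44.
- If the sole carrier is a completer instead (0/4 versus 1/16): Pearson p = 0.61, Fisher p = 1.00.

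**4. Sensitivity to the number of dropouts (sole carrier, a dropout).**

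| Dropouts vs completers | Pearson p | Fisher p |
|---|---|---|
| 2 vs 18 | 0.002 | 0.10 |
| 3 vs 17 | 0.015 | 0.15 |
| 4 vs 16 | 0.040 | 0.20 |
| 5 vs 15 | 0.076 | 0.25 |

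A second pattern at 4 versus 16 also crosses 0.05: 2/4 versus 1/16 gives Pearson 0.028 and Fisher 0.088. By contrast, 2/4 versus 0/16 gives 0.003 and 0.032, so there the tests agree on which side of 0.05 the result falls.

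**5. Actual size at 4 versus 16.** Every table was enumerated under no association, weighted by Bin(a; 4, π) × Bin(b; 16, π), and the weight with p < 0.05 was summed. Tables with no carriers, or only carriers, count as no rejection.

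| Prevalence π | 5% | 10% | 20% | 30% | 50% |
|---|---|---|---|---|---|
| Pearson, uncorrected | 8.7% | 8.3% | 5.1% | 4.1% | 5.6% |
| Fisher | 0.6% | 1.2% | 1.5% | 1.4% | 1.4% |
| Yates | 0.6% | 1.1% | 0.9% | 0.7% | 0.5% |

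At 5% prevalence most of the excess comes from single-carrier tables. The chance of exactly one carrier is 20 × 0.05 × 0.95¹⁹ = 0.377, and 0.377 × 0.20 = 0.075 of the total 0.087.

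**6. Enrollment comparison.** If 70% of eligible patients enroll, as in Table 1, then 20/0.7 ≈ 29, giving 20 enrolled versus about 9 not. Uncorrected Pearson then has size 2.9%, 4.5%, 5.1%, 5.2% and 5.0% at the same prevalences. Individual tables can still disagree: 2/9 versus 0/20 gives Pearson 0.029 and Fisher 0.089.

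**The case against.** The case against has several parts.

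- **The p of 0.040 is conditional.** It needs the uncorrected Pearson test, exactly 4 dropouts, and a carrier who dropped out. With one carrier and no association, that person is a dropout only 20% of the time. Under Yates the inflation disappears. This stands as a limit on the claim. It does not remove the point, because the plan leaves the version open.
- **Rarity is assumed.** The documents do not say that pregnancy-associated SCAD or psychiatric comorbidity is uncommon in this population. At 20% to 50% prevalence the size is 4% to 6%, which is acceptable. This stands.
- **The inflation depends on the split.** With 5 dropouts versus 15, the uncorrected size is about 1% to 5% over the same prevalences, so there is no material excess. This stands.
- **The enrollment comparison is not inflated** at 20 versus 9. This stands, so the case for a blanket change rests on the dropout comparison alone.
- **The comparison is secondary.** No benchmark, sample size or progression decision uses it. This stands and keeps the point minor.

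A reader might also infer that a spurious dropout predictor would steer the refinement of the intervention between the two groups. The documents do not support that. The Adapted MBCT intervention section places refinement after the first group, whereas 4 versus 16 exists only once both groups have finished. Nothing says that dropout comparisons feed the refinement; the input named in Table 1 for program improvement is the exit interview.

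**Conclusion.** The point holds in a limited form and is minor. The plan names a test whose approximation is not reliable at about 4 versus 16, and no safeguard in the document covers it. For an uncommon trait the uncorrected version can turn one person into p = 0.040 when the exact value is 0.20. Its false-positive rate at a nominal 5% is about 8% to 9% at 5% to 10% prevalence.

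This rests on 4 dropouts out of 20, completers as comparator, uncorrected Pearson, an assumed 5% level and assumed rarity of the trait. It should not be read as saying that every rare trait will appear significant, or that chi-square fails for the enrollment comparison in general. The feasibility and acceptability benchmarks do not depend on it.

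**What to change.** In the Analysis Plan for Aims 1 and 2, replace chi-square with Fisher's exact test for categorical comparisons of dropouts with completers, and for any enrollment comparison with small expected counts (for example, any below 5). Name completers as the comparison group. For each comparison report the counts and the difference in proportions with an exact or score confidence interval, and base the interpretation on the interval.

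The cost is a sentence in the plan and one interval per comparison; no new data or procedures are needed. The downside is that Fisher's test is conservative here, with actual size of about 1%, so a non-significant result says little. Reporting counts alone, without a test, would also be defensible for the dropout comparison.

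### The Aim 3 model for daily diary and actigraphy outcomes needs 17 fully observed participants at 16 time levels (15 at 14 levels), more than the trial's own retention and completion targets secure, and its pre-post question waits on an unreliable omnibus time test

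*Combined protocol and SAP*

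**What the plan says.** The Analysis Plan proposes, for each psychological and behavioral variable separately, "linear mixed effects models with repeated measures and an unstructured covariance matrix to assess changes over time". Time is a fixed effect with "up to 16 levels across pre-post intervention surveys and daily diaries or actigraphy". The other predictors are "covariates relevant for each dependent variable (random effects"). The comparison of interest is conditional: "If there are any time effects, we will conduct follow up analyses", and those follow-up analyses are what establish whether change over the intervention went in the expected direction. Interpretation is to rest on "effect sizes (Cohen's d) rather than statistical significance". Missing data are handled by maximum likelihood, with last observation carried forward as a sensitivity analysis. No fallback covariance structure, non-convergence rule or degrees-of-freedom method is given.

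Research Design and Methods plans about 20 participants in two groups of about 8, "accounting for 20% anticipated lost to follow-up". The Daily Diary and Actigraphy sections give about 7 days before and 7 after the intervention. Table 1 (Measured Outcomes) sets the actigraphy target at "≥70% completed 7 consecutive days", sets the same 70% for diaries, and tolerates "≤20% missing data on daily diaries". The remuneration text in Recruitment Procedures pays for 80% of actigraphy days and 80% of diaries.

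**The concern.** An unstructured matrix over 14 or 16 occasions is very large for about 20 people. If too few have complete records, the stated model has no maximum likelihood solution, and whatever model is reported must be picked after the data are in. The trial could meet every feasibility target and still be unable to fit its own Aim 3 model for the daily outcomes.

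Separately, the question the pilot wants answered is whether outcomes differ after the intervention from before. That is a single contrast, but it is reached only through a global test that any of 14 or 16 occasion means differ. With so few people, that test either rejects far too often or rarely, depending on a df method the plan does not name.

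A smaller point is that covariates with one value per person, such as pregnancy-associated SCAD or the SCAD date, are labelled random effects. They would sensibly be fixed effects.

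**Working it through.** **Scope.** This applies to daily diary and actigraphy outcomes, taking the unstructured matrix to be the within-person covariance across occasions. That is the natural reading, though the plan does not say so.

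**1. The plan's own figure.** Two groups of 8 give 16. Allowing for 20% loss, 16 / 0.8 = 20 enrolled, which reproduces the plan. Expected completers are 20 × 0.8 = 16, and the 70% target is 20 × 0.7 = 14.

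**2. Covariance parameters, T(T+1)/2.**
- T = 16 (14 days plus two surveys): 136
- T = 14 (daily data only): 105
- T = 2 (surveys only): 3

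**3. Complete participants needed.** With T separate means, n complete participants give a sample covariance of rank at most n − 1. If n ≤ T, some linear combination of the occasions is constant across all of them, and shrinking the variance along it sends the likelihood to infinity. So n must be at least T + 1: 17 for 16 levels and 15 for 14.

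Participants with a missed occasion do not rescue the fit. In simulated data with 20 participants, shrinking the variance along that direction 100-fold at a time gave:
- 16 levels, 16 complete and 4 partial: log-likelihood −376.6, −340.1, −303.3, −266.5, still rising
- 14 levels, 14 complete and 6 partial: −348.1, −326.8, −294.9, −262.6, still rising
- 17 complete (16 levels) or 15 complete (14 levels): it falls away, as it should

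Each person-level fixed covariate adds one to the requirement, so one covariate makes it 18 or 16.

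**4. Against the plan's figures.** At 16 levels, 16 expected completers is one short. At 14 levels, 16 suffices by one, so at most one completer may miss a day. The 14-of-20 target falls short in both cases. Full payment at 80% of 14 days (11.2) is earned with 12 days.

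**5. Chance of enough complete records, binomial with n = 20.**

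| Probability that a participant is complete | 16 levels, P(≥17) | 14 levels, P(≥15) |
|---|---|---|
| 0.8 (80% retained, no missed occasion) | 0.41 | 0.80 |
| 0.7 (Table 1 target) | 0.11 | 0.42 |
| 0.8 × 0.99^T (assumed 1% missed at random) | 0.08 | 0.40 |
| 0.8 × 0.98^T (assumed 2% missed at random) | 0.01 | 0.13 |

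**6. The omnibus test where the model can be fitted.** The exact (Hotelling) test has df (T−1, N−T+1). If the Wald F is referred instead to N−1 denominator df, its true size is P{F(T−1, N−T+1) > F.95(T−1, N−1) × (N−T+1)/(N−1)}:
- 16 levels, N = 20: 0.80
- 14 levels, N = 16: 0.84
- 14 levels, N = 20: 0.63

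The exact test holds 5% but has few denominator df. Power is shown below under assumptions that are not in the documents: day-level SD 1, a constant post-intervention shift of 0.5, within-person correlation 0.5, and between-person variance of the change of 0 or 0.25. The post-minus-pre contrast then has per-person variance 2(1 − 0.5)/7 = 0.143 at 14 levels, plus 0 or 0.25. The noncentrality at N = 16 is 16 × 0.25 / 0.143 = 28, or 16 × 0.25 / 0.393 = 10.2.

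| Levels, N (all complete) | Exact omnibus, change variance 0 / 0.25 | 1-df contrast, 0 / 0.25 |
|---|---|---|
| 14, 16 | 0.22 / 0.11 | >0.99 / 0.85 |
| 14, 20 | 0.57 / 0.22 | >0.99 / 0.92 |
| 16, 20 | 0.44 / 0.16 | >0.99 / 0.93 |

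Over shifts of 0.3 to 0.8, correlations of 0.3 to 0.7 and change variance 0 or 0.25, the exact omnibus power is 0.07 to 0.67 (14 levels, N = 16) and 0.08 to 0.97 (16 levels, N = 20). The contrast gives 0.39 to >0.99 and 0.50 to >0.99, and is higher in every case.

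**The case against.** The arithmetic is not in dispute. The case against concerns scope and weight.

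- **At 14 levels, 16 completers exceed the 15 required.** True. Failure there needs two or more completers with a missed day, or completion near the 70% floor. Actigraphy has only 14 occasions, and a 16-level diary outcome would pool full survey scales with one- or two-item diary versions, so 14 levels may be the commoner case.
- **The inputs are approximate.** Enrolment, group size and days are all given as approximate, 70% is a minimum rather than an expected rate, and Table 1 does not define its denominator. This stands, but it does not rescue the model: 70% of 16 retained would be 11.2, which is worse. The 1% and 2% missed-occasion rates are assumptions.
- **No F test or alpha is named, and effect sizes take precedence.** Also true. Even so, making follow-up conditional on a time effect reads naturally as a gate on the multi-level factor, and an effect size still needs a model that can be fitted. The survey change scores and their correlations are not gated.
- **The power comparison assumes a step change, which is what the contrast targets.** Fair. It says nothing about effects that vary by day. A step from before to after is, however, the hypothesis the plan states.
- **Other provisions might help.** Non-parametric tests are offered in response to distributions, not non-estimability. Carrying values forward can fill the matrix, but with artificial values and only as a sensitivity analysis.
- **Aim 3 is exploratory.** This limits the severity. It does not make the stated model fittable.

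**Conclusion.** The concern holds and should be fixed. As written, the model for daily outcomes cannot be fitted at 16 levels with the expected 16 completers, and at 14 levels it has a margin of one person. With 20 enrolled, the chance that it can be fitted is 0.41 (16 levels) or 0.80 (14 levels) at 80% retention with perfect diaries, and 0.11 or 0.42 at the completion rate the plan would call success. This rests on the within-person reading of the matrix and on independent participants with a common completion probability.

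The gate is a second defect that remains even with 20 complete records. Whether a pre-post change is followed up would turn largely on an unstated df method. The power figures depend on the assumed shift, correlation and step pattern; the type I errors depend only on T, N and the uncorrected N−1 df, under normality. The random-effects label for person-level covariates is minor.

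The primary feasibility and acceptability outcomes and the two-occasion survey models are untouched. What is at risk is the intervention signal that the pilot is meant to provide from its daily measures.

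**What to change.** For diary and actigraphy outcomes:

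- Replace the multi-level time factor with a two-level phase effect (post versus pre).
- Replace the unstructured matrix with a parsimonious covariance, for example a participant random intercept plus random phase effect, or a random intercept with AR(1) within phase.
- Name the fallback in advance: random intercept only, if the phase variance is estimated at zero.
- Name a small-sample df method such as Kenward-Roger.
- Enter one or two named baseline covariates as fixed effects.
- Report the 1-df post-minus-pre difference with 95% CI and Cohen's d for every outcome, and delete the condition that a time effect must first be found.

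Keep the unstructured matrix for the two-occasion survey models only.

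The cost is rewording one paragraph of the Analysis Plan, with no new data. The downside is that the model assumes a simple correlation pattern within each window and does not describe day-by-day trends.

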#### **Data collection:**

Study assessments include a battery of pre-post self-report surveys administered at baseline and post-intervention; post-intervention individual exit interviews (conducted via telephone or videoconference), and daily diary surveys and actigraphy assessments (sleep and physical activity) collected for 7 days within the 1-2 weeks before and after the intervention. All study surveys and daily diaries may be completed via REDCap, email, or paper mail, depending on patients' preferences. Data collection will also consist of viewing and extracting data from the EHR of enrolled participants to assess medical and demographic variables (e.g., medical diagnoses, medications, cardiac rehab attendance).

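### The only missing-data sensitivity analysis for Aim 3 stops at no change for people who leave, so no planned analysis shows the effect size if leavers got worse

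*Combined protocol and SAP*

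**What the plan says.** The Analysis Plan sets two methods for missing Aim 3 data. The main one is maximum likelihood: "Missing data will be imputed using maximum likelihood estimation". The second is "as a sensitivity analysis, the last observation carried forward". No other missing-data analysis is named anywhere in the document. The plan also compares dropouts with others on demographic and clinical variables, but that comparison is descriptive.

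Three other places bear on the point:

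- **Timing.** Under Data collection, the survey battery is "administered at baseline and post-intervention". Diaries and actigraphy are likewise confined to the weeks before and after the intervention.
- **Expected loss.** Research Design and Methods plans about 20 participants in two groups of about 8, "accounting for 20% anticipated lost to follow-up". Table 1 sets the retention benchmark at "≤20% participant attrition".
- **Reasons for leaving.** The safety text that follows the Analysis Plan states: "The objective criteria for removal from the study is worsening psychiatric symptoms", where these become unstable enough to preclude participation. It also gives people who worsen short of that point the option to exit.

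The Analysis Plan calls Aim 3 exploratory and reads it through Cohen's d rather than significance.

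**The concern.** A sensitivity analysis should show how far the result moves if the main assumption about missing data fails in a plausible direction. Maximum likelihood assumes that, given the observed pre-intervention data, leavers would have changed as completers did. The protocol itself foresees one way for this to fail: people may leave because their psychological symptoms worsen, in the domain that Aim 3 measures. Nothing in the document provides for post-intervention outcomes from people who are removed.

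Carrying the last value forward tests one alternative only, zero change. If some leavers deteriorated, both planned analyses can lie on the optimistic side, and the report would contain nothing to show it. What is at stake is the size of the Cohen's d that the plan will use as a signal of intervention effect.

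**Working it through.** **1. The plan's own figure.** Two groups of 8 give 16 completers. With 20% loss, enrolment is 16 / (1 − 0.20) = 20, as stated. The anticipated loss is therefore 4 people.

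**2. Assumptions, none of them in the documents.** Completers improve by 0.5 baseline SD. The pre-post correlation is 0.5, so the SD of change is √(2 × (1 − 0.5)) = 1. Let c be the mean change of the 4 leavers, with positive meaning improvement.

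**3. Mean change.**

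- Truth: (16 × 0.5 + 4 × c) / 20 = 0.40 + 0.2c
- Likelihood: 0.50, whatever c is (leavers assumed similar to completers at baseline)
- Carried forward: (16 × 0.5 + 4 × 0) / 20 = 0.40, whatever c is

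| Leavers' mean change c | Truth | Likelihood | Carried forward |
|---|---|---|---|
| +0.5 | 0.50 | 0.50 | 0.40 |
| 0 | 0.40 | 0.50 | 0.40 |
| −0.5 | 0.30 | 0.50 | 0.40 |
| −1.0 | 0.20 | 0.50 | 0.40 |

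Carrying forward overstates benefit only when c is below zero, by 0.2 × |c|. In the last two rows it is 0.40 / 0.30 = 1.33 and 0.40 / 0.20 = 2 times the truth.

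**4. If only one leaver worsens.** Suppose one of the four worsens by 1.0 SD. If the other three are unchanged, the truth is (8 − 1) / 20 = 0.35, below 0.40. If the other three improve like completers, it is (19 × 0.5 − 1) / 20 = 0.425, and carrying forward is then slightly pessimistic.

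**5. Standard error.**

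- 16 real pairs: 1 / √16 = 0.250, so t = 0.50 / 0.250 = 2.00.
- Carried forward, 20 values of which four are zeros: sum of squares = 15 × 1 + 16 × 0.5² − 20 × 0.40² = 15.8. SD = √(15.8 / 19) = 0.912 and SE = 0.912 / √20 = 0.204, so t = 0.40 / 0.204 = 1.96.
- Ratio: 0.204 / 0.250 = 0.82, a reduction of 18%.
- Standardised by the SD of change, d falls from 0.50 to 0.40 / 0.912 = 0.44.

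For completer effects of 0.2, 0.8 and 1.2 the SE ratio is 0.80, 0.85 and 0.91.

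**6. Coverage.** In 40,000 simulated trials with c = −1.0, the nominal 95% carried-forward interval covered the true mean 87% of the time at a correlation of 0.5, and 80% at 0.7.

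**The case against.** The strongest reply is that carrying forward already moves the estimate the right way. In a single-arm pre-post design it pulls 0.50 down to 0.40 and d down to 0.44. This stands. A reader might infer that the method flatters the result relative to the main analysis; the arithmetic shows the opposite. What remains is that it stops at zero.

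A reader might also infer from the smaller standard error that false significance follows. It does not: the mean shrinks with the standard error, and t goes from 2.00 to 1.96. The plan does not rest Aim 3 on significance in any case.

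Nor do the documents support treating the anticipated 20% loss as removal for worsening. That figure is general loss to follow-up, and participants may withdraw without giving a reason. Severe mental illness needing urgent intervention is an exclusion, the removal threshold is narrow, and no expected number is given for either route tied to worsening. The rows with all four leavers worse are therefore illustrations, not forecasts.

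Finally, exact zero change applies to the surveys. For diaries and actigraphy, someone who leaves during the intervention carries the last pre-intervention day, which need not equal that week's mean, and someone who stops during the later week carries a post-intervention value.

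**Conclusion.** The point holds as a limited one. Last observation carried forward is the only missing-data sensitivity analysis named. For the pre-post surveys it fixes a leaver's change at zero and treats the copy as data. It is more cautious than likelihood, but neither analysis covers deterioration, which the protocol itself links to leaving. On the stated assumptions, the planned analyses report 0.40 to 0.50, while the truth could be 0.30 or 0.20 if every leaver worsened by 0.5 or 1.0 SD. With fewer worsening, the gap is smaller or absent.

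The consequence is modest: Aim 3 is exploratory, the primary outcomes are feasibility and acceptability, and attrition is itself reported against a benchmark. This is a cheap improvement, not a flaw that undermines the trial.

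**What to change.** For the pre-post survey outcomes, at least fear-of-recurrence severity and cardiac anxiety, replace carrying forward with a delta-adjusted analysis. Impute missing post-intervention scores by multiple imputation from baseline, shift them in the unfavourable direction by 0, 0.5, 1.0 and 1.5 baseline SD, and report Cohen's d with its 95% CI at each shift. State the unfavourable direction for each scale in advance.

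The 1.5 SD step is needed. In the example, imputed leavers start at about +0.5, so the four shifts place them at +0.5, 0, −0.5 and −1.0, giving means of 0.50, 0.40, 0.30 and 0.20. The 0.5 SD shift only reproduces the carried-forward mean, so a range ending at 1.0 would go just one step past no change.

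The cost is a short addition to the Analysis Plan and somewhat more programming: two outcomes at four shifts make eight results. The shift sizes are assumptions, but they are stated openly. Data collection and the rules for leaving the study are untouched.
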